2.4 Study Rationale

The current standard dose for decitabine in MDS and AML is 20 mg/m² daily x 5 days. A study conducted by the Ohio State University has produced significantly higher response rate when an extended schedule of decitabine 20 mg/m² daily x 10 days was used. The objective of the study is to demonstrate whether this extended 10 day schedule is superior compared to the standard 5 days schedule in producing responses and at least comparable with regards to toxicity and response duration.

3.0 Decitabine

3.1 Chemical Name

- 4-amino-1-(2-deoxy-ß-D-erythro-pentofuranosyl)-1,3,5-triazin-2(1H)-one
- Other Names: deoxyazacytidine, 5-aza-2'-deoxycytidine, 1-(2'-deoxy-D-ribofuranosyl)-5azacytosine, DAC, 5-Aza-CdR, dezocitidine
- Classification: Antimetabolite, DNA hypomethylating agent
- Molecular Formula: C8H12N4O4 M.W.: 228.21
- Approximate Solubility: Slightly soluble in water (25mg/mL), ethanol and virtually insoluble in chloroform

3.2 Mode of Action: Hypomethylation of DNA followed by stimulation of gene expression and cell differentiation. Inhibits DNA methyltransferase. Targets for latter mechanism are selected genes silenced by DNA methylation. Inhibits DNA synthesis

3.3 How Supplied: Decitabine is supplied as a lyophilized white to almost white, finely crystalline, odorless powder for injection in 20mL vial glass vials, containing 50 mg of decitabine, monobasic potassium phosphate, and sodium hydroxide.

3.4 Preparation: When reconstituted with 10 mL of sterile water for injection each mL will contain 5 mg of decitabine, 6.8 mg of KH2PO4, and approximately 1.1 mg NaOH. The pH of the resulting solution is 6.5 - 7.5.

The reconstituted solution can be further diluted to a concentration of 1 mg/mL or 0.1 mg/mL in cold infusion fluids (0.9% Sodium Chloride Injection USP, 5% Dextrose in Water Injection, USP, or Lactated Ringer's Injection USP).

3.5 Storage and Stability: Vials should be stored at 25°C (77°F); excursions permitted to 15°C to 30°C (59°F to 86°F). After reconstitution, use decitabine within 15 minutes. If diluted with cold (2°C to 8°C) fluids, the diluted solution is stable for up to 7 hours if stored between 2°C and 8°C (36°F to 46°F).

Reconstitution and dilution of the powder for injection (with 10mL of sterile water for injection) results in a rapidly decomposing solution. The concentration of decitabine in the reconstituted and diluted solution decreases about 10 % after 4 hours at 25°C or about 10% after 24 hours at 4°C. Since 10% is the maximum allowable decomposition, and the solution will also decompose during administration (infusion), the solution should be prepared just prior to administration. If this is not possible the solution should be prepared at least twice a day and kept in a refrigerator (2-8°C) until administration. Furthermore, the solution should be prepared only with cold infusion fluids at a temperature of 2-8°C; (36-46°F). This solution can be infused over a maximum period of 3 hours.

3.6 Route of Administration: Intravenous

3.7 Precautions

Drug handling precautions will be strictly followed. Skin contact with the solution should be avoided and protective gloves should be worn. Drug spilling can be inactivated by 2 M sodium hydroxide solution. The skin should be treated with a borax buffer solution pH 10 and after that thoroughly washed with water and soap.

3.8 Drug supply and distribution: Decitabine will be obtained from commercial source.

3.8 Reported Adverse Events and Potential Risks

Autoimmune reaction and/or chemical imbalances in the blood (antiplatelet antibodies, erythema nodosum), decreased hemoglobin, decreased leukocytes (total WBC), decreased neutrophils/granulocytes (ANC/AGC), decreased platelets, drowsiness, fatigue (lethargy, malaise, asthenia), alopecia, diarrhea, peritonitis, nausea, vomiting, anorexia, stomatitis/pharyngitis (oral/pharyngeal, mucositis), increase bilirubin, increased SGOT (AST) (serum glutamic oxaloacetic transaminase), increased SGPT (ALT) (serum glutamic pyruvic transaminase), liver damage, depressed level of consciousness, abdominal pain or cramping.

Also reported on Decitabine trials but with the relationship to Decitabine still undetermined: allergic reaction; allergic rhinitis; GVHD; bone marrow cellularity; atrial fibrillation; cardiac ischemia/infarction; cardiopulmonary arrest; hypotension; left ventricular systolic dysfunction; right ventricular dysfunction; fever; insomnia; rigors/chills; weight loss; pruritus; rash; anal ulcer; ascites; constipation; distension; esophagitis; GI obstruction; ileus; taste alteration; CNS hemorrhage; GI hemorrhage; lung hemorrhage; nose hemorrhage; petechiae; urinary hemorrhage; cholecystitis; liver dysfunction/failure; infection without neutropenia; opportunistic infection; perianal abscess; head/neck edema; alkaline phosphatase; creatinine; hypercalcemia; hyponatremia; fracture; agitation; CNS ischemia; confusion; depression; dizziness; extrapyramidal/involuntary movement; motor neuropathy; psychosis; seizure; sensory neuropathy; bone pain; headache; muscle pain; urinary pain; ARDS; bronchospasm; cough; dyspnea; hiccoughs; pneumonitis/pulmonary infiltrates; cystitis; renal failure; urinary frequency; phlebitis; thrombosis/thrombus/embolism; venoocclusive disease.

4.0 Eligibility Criteria

4.1 Inclusion criteria

- Patients with previously untreated AML (by the WHO criteria, i.e.≥ 20% blasts) Prior biologic therapies (such as growth factors) and targeted therapies administered for the treatment of prior myelodysplastic syndrome are allowed, with the exception of hypomethylating agents 5-azacytidine or decitabine. Patients must have been off such therapy for 1 week prior to entering this study and recovered from the toxic effects of that therapy, unless there is evidence of rapidly progressive disease. Hydroxyurea, and a single dose of cytarabine up to 3 g/m², is permitted for control of counts prior to treatment.
- Patients ≥ 60 are eligible if not a candidate for standard cytarabine plus anthracycline chemotherapy as determined by Kantarjian's score (Appendix D) Patients younger than 60 may also be included if felt not to be a candidate for intensive anthracycline plus cytarabine based chemotherapy.
- 3. Performance 0-3 (ECOG).

- Adequate liver function (Total bilirubin of < 2 mg/dl) unless due to hemolysis, leukemia organ infiltration or Gilbert's syndrome and renal function (creatinine < 2.5 mg/dl).
- 5. Signed informed consent

4.2 Exclusion Criteria

- 1. Nursing and pregnant females. Female patients of childbearing potential and male patients should practice effective methods of contraception such as double barrier method. Should a woman become pregnant or suspect she is pregnant while participating in this study, she should inform her treating physician immediately. Negative urine pregnancy test (women of childbearing potential)
- 2. Active and uncontrolled infections.
- 3. Uncontrolled intercurrent illness including, but not limited to, symptomatic congestive heart failure, unstable angina pectoris, active significant other cancers requiring chemotherapy and/or radiation therapy within past 6 months (excluding non-melanoma skin cancer) or psychiatric illness/social situations that would limit compliance with study requirements.

5.0 Therapy

5.1 **Protocol registration:**

All patients will be registered through the Protocol Data Management System (PDMS) or Clinical Oncology Research (CORe). The study chairman must be notified before any patients are registered.

5.2 Therapy

The initial Decitabine courses should be given at MD Anderson Cancer Center (or Regional Cancer Centers), either as in-patient or as out-patient. Decitabine will be dosed based on actual body weight. However, at the treating physician's discretion an adjusted body weight may be used, if actual body weight is >40% over ideal body weight. Adjusted body weight = ((Actual body weight – Ideal body weight) 0.4) + Ideal body weight. Decitabine may be subsequently administered at any of the Regional Cancer Centers (RCC) or at the patients' local oncologist offices. Patients will be assigned in a selective Bayesian design to one of two treatment arms.

- 1) Decitabine 20 mg/m² IV over approximately 1 hour daily x 5.
- 2) Decitabine 20 mg/m² IV over approximately 1 hour daily x 10.

Start at dose level 0 as shown below. There will be no dose escalation of Decitabine.

Patients will receive one course every 4-8 weeks; however delays of more than 8 weeks may be allowed if determined by the investigator to be in the best interest of the patient after discussion with the PI and the discussion documented in the patient's medical record. Doses may be given as close as 8 hours apart if approved by the PI. If prolonged aplasia and/or a major infection is seen, may decrease 1 dose level after marrow regeneration. This will be rounded to the following daily lower dose (15, 10, 7.5, 5 mg/m²). Otherwise continue at the same dose level every 4-8 weeks depending on recovery of counts and disease status. If persistent disease, start next course regardless of counts. If marrow complete response is achieved with adequate cellularity, start subsequent courses when granulocytes $\geq 0.75 \times 10^9$ /L and platelets $\geq 50 \times 10^9$ /L.

Patients on the 10 day regimen will receive 5 day dosing after achieving CR during consolidation/maintenance. The 5 day dosing may also be initiated in these patients after the first course, if it is thought to be in the best interest of the patient after discussion with the PI and the discussion documented in the patient's medical record. Patients on the 5 day regimen will continue to receive the 5 day regimen after the first course whether in CR or not.

Modifications of dose schedule or dose level other than above are allowed if felt to be in the patients best interest to optimize response or reduce toxicity. These decisions should be documented in the patient's medical record.

	Decitabine mg/m ²	² daily x days
Dose level	10 days	5 days
0	20	20
-1	15	15
-2	10	10
-3	7.5	7.5
-4	5	5

5.3 Duration of Therapy

In the absence of treatment delays due to clinically significant study drug related adverse events, treatment may continue until one of the following criteria applies:

- Relapsed or clinically significant progressive disease; no response after
 > 3 courses.
 Patients may continue therapy as long as they have stable disease, as long as it is
 determined to be in the best interest of the patient.
- Intercurrent illness that prevents further administration of treatment,
- Patient decides to withdraw from the study, or

- General or specific changes in the patient's condition render the patient unacceptable for further treatment in the judgment of the investigator.
- Up to a total of 24 courses of therapy; about 2 to 3 years.

a. Patients who show no evidence of life-threatening infection or hemorrhage, or less than grade 2 clinically significant drug related non-hematologic toxicity (vomiting included) may be given a subsequent course at the same dose as the previous course. If clinically significant drug-related grade 2 toxicity is observed, the patient must have recovered to grade ≤ 1 before institution of the next course. If patients have clinically significant drug-related grade 3-4 non-hematologic toxicity, they may receive a subsequent course at one reduced dose level after resolution of toxicity to \leq grade 1.

b. Patients with a response (defined under section 10.0) and pre-course counts of granulocytes $>10^{9}/L$ and platelets $>50 \times 10^{9}/L$ who have sustained low counts of granulocytes $<0.5 \times 10^{9}/L$ or a platelet count $<30 \times 10^{9}/L$ for more than 2 consecutive weeks in the current cycle, may receive a subsequent course at 1 dose level reduction. A reduction of 2 dose levels may be considered if the myelosuppression was deemed severe and life threatening by the treating physician, and if it is in the patient's best interest.

c. Patients may receive further courses of therapy not earlier than 4 weeks from the previous course, provided the patient has recovered from myelosuppression considered to be related to chemotherapy. Patients with rapid increase in blasts may start additional therapy before 28 days from start of the previous course.

d. A minimum of 1 full course (or 4 weeks from the start of therapy) will be required for a patient to be considered as having received an adequate trial to evaluate efficacy. All patients receiving at least one dose of decitabine will be considered evaluable for toxicity. Patients achieving a partial response or with stable disease may continue on therapy until definite evidence of disease progression.

e. Patients who achieve CR or CRi may be treated with additional courses of decitabine every 4-8 weeks or longer if approved by the PI. The dose of decitabine can be adjusted down by one dose level for toxicity (see above). Patients may be taken off study or treated on other programs (e.g. bone marrow transplantation) if this is judged more appropriate for their therapy and overall outcome. Delays of more than 8 weeks to subsequent course may be allowed if determined by the investigatory to be in the best interests of the patient after discussion with the PI and the discussion documented in the patient's medical record. Abnormalities in chemistries including BUN, LDH (lactic dehydrogenase), alkaline phosphatase, magnesium, glucose, phosphorus, calcium and electrolytes will not be reported as adverse events. These are indications of disease process and not of toxicity, therefore clinically insignificant. Delayed recovery in patients post CR is common in MDS and AML not associated with significant clinical complications such as bleeding or infections. Therefore, delayed myelosuppression after a course in CR will be

5.4 Concomitant medications

GCSF or other growth factors are permitted on therapy only as per ASCO guidelines. Use of hydroxyurea with rapidly proliferative disease is allowed for the first two weeks on therapy.

6.0 Correlative studies

One of the goals of this protocol is to measure the biological effect of epigenetic therapies. Several correlative laboratory studies will be carried an attempt to assay the biological effect of decitabine. Patient samples including peripheral blood and bone marrow will be collected prior to, during and after completion of treatment.

6.1 Gene-mutations effecting methylation machinery

Mutations of several genes believed to be important in the methylation apparatus of the cell have been recently described in patients with acute myeloid leukemia (AML) but their presence has not been correlated with a worse or better outcome using hypomethylating agents. We have previously evaluated the association of mutations in IDH1. IDH2. DNMT3A. and EZH2 with the outcome [complete response (CR) rate, event free survival (EFS) and overall survival (OS)] among patients older than 60 with AML (≥ 20% blasts) treated with hypomethylating agents as their first line of treatment. TET2 mutations were not evaluated due to lack of available material. Among the 68 patients (median age 72 years; range, 60 - 83) with available data, 11 patients (16%) had IDH1 or IDH2 mutations (mutually exclusive) and 10 patients (15%) had DNMT3A mutations with 5 patients (7%) having both IDH and DNMT3A mutations. Cytogenetics was diploid in 19 (28%), abnormal chromosome 5/7 and/or complex in 27 (40%), trisomy 8 in 5 (7%), miscellaneous in 14 (21%), and insufficient in 3 (4%). Presence of *IDH* mutations was associated with a diploid karyotype and the presence of *NPM1* mutations (p=.03 and p=.02, respectively) but not with FLT3-ITD or RAS mutations (present in 7 and 4 patients, respectively). DNMT3A mutations were not associated with any specific karyotype or with the presence of NPM1, FLT3-ITD, or RAS mutations. None of the 68 patients had EZH2 mutations. All patients were treated with hypomethylating agents [decitabine in 39 (57%) and 5-azacytidine in 29 (43%)] with 42 patients (62%) receiving concomitant histone deacetylase inhibitor therapy (SAHA or valproic acid). Overall, 17 patients (25%) achieved CR; the presence of IDH or DNMT3A mutations or both was not associated with achievement of CR. With a median duration of follow-up of 60 months, the median EFS is 3.3 months (range, 0.25 - 3.75 months) and the median overall survival is 6 months (range, 0.25 - 90.5 months). Presence of IDH mutations was not associated with an impact on EFS (p=.29) or OS (p=.14). Similarly, DNMT3A mutations were not associated with an effect on EFS (p=.21) or OS (p=.58). The presence of both IDH and DNMT3A mutations was also not associated with a better or worse response, EFS, or OS as compared with patients with neither mutation. We

May 24, 2017 Page **18** of **29** were unable to detect an association between presence of *IDH1/2* and *DNMT3A* mutations and outcome in this elderly population of patients with AML treated with epigenetic modulators.

2012-1017

In this study we propose to evaluate the potential effect of mutations of 1DH1, IDH2, DNMT3A, TET2, EZH2 and other genes believed to be in the DNA methylation program prospectively by assessing the patients for the presence of these mutations prior to the initiation of therapy. We will also examine follow-up samples to determine if the leukemic blasts harboring these genes remain after therapy.

Using more sophisticated assessments of gene panels and whole exome sequencing we will expand this prospective evaluation and will determine if certain gene signatures are associated with response.

We will also evaluate the levels of 2-hydroxyglutarate in patients with DNMT3A mutation and will determine if there is any association with response to therapy and outcome.

6.2 Gene specific methylation.

The proposed mechanism of action of hypomethylating agents such as decitabine is through their action against DNA methyltransferase enzymes responsible for methylation of promotor regions (and hence silencing of) genes responsible for differentiation. We will examine this hypothesis though the examination of gene-specific and global methylation of the leukemic cell genome pre and post therapy. Quantitative methylation analysis of the p15 promoter and other genes, including Alu elements will be performed using "COBRA" analysis (Combined Bisulfite and Restriction Analysis). This technique takes advantage of the ability of bisulfite to selectively convert cytosine to uracil, but without affecting 5-methylcytosine. Thus DNA can be treated with bisulfite, amplified by PCR, and the PCR product digested with restriction enzymes which will quantitatively assess gene specific methylation depending on the converted DNA sequence.

6.2.1 Assessment of genome wide methylation. Total genome DNA methylation can be measured using high pressure liquid chromatography and assaying directly for 5-methylcytosine. This technique however requires large amounts of DNA sample (approximately 50ug).

Therefore COBRA analysis described above will be used to assess methylation of genes and Alu repetitive elements in the patient samples. Alu elements are short DNA repeats which litter the genome. It is estimated that there are one million Alu's in the human genome. These elements are also heavily methylated, and therefore allow the opportunity to simultaneously study demethylation of one million sites in the genome rather than a single gene.

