7.0 Pre-study evaluations (to be performed within 14 days unless otherwise noted)

- 7.1 History and physical exam.
- 7.2 CBC, platelet count, differential; creatinine, bilirubin, SGPT (within 7 days).
- 7.3 Bone marrow aspirate (within 14 days) and cytogenetics
- **7.4** Molecular studies in bone marrow specimens for FLT3-ITD, FLT3-TKD, NPM1, IDH1, IDH2, DNMT3A, TET2, EZH2, RAS, JAK2 (if appropriate, e.g. in patients

with history of MPN), and the Leukemia mutation panel (whichever is available at the time of enrollment)

- 7.5 Whole genome sequencing (performed at [name] laboratory)
- **7.6** Blood sample (20-50 cc) and marrow aspirate sample (2 cc) for methylation studies, to be sent to [name] laboratory. Not all samples may be collected at all times points and omissions will not be considered deviations. Samples obtained prior to consenting may be used.
- **7.7** Blood sample (25-35cc) will be collected for assessment of immune function and effector cells to be sent to [name] lab. Not all samples may be collected at all times points and omissions will not be considered deviations. Samples obtained prior to consenting may be used.
- **7.8** Pregnancy (urine or blood) test only for women of childbearing potential within 7 days.

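### Section 6.1 restricts 2-hydroxyglutarate measurement to DNMT3A-mutated patients, although mutant IDH1/IDH2 produces this metabolite; probably a gene-name slip in an exploratory correlate

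*Combined protocol and SAP*

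**What the plan says.** Section 6.1 plans a prospective look at mutations in genes of the methylation machinery and adds one sentence on a metabolite: "We will also evaluate the levels of 2-hydroxyglutarate in patients with DNMT3A mutation". The levels are then to be related to how patients respond and fare. This is the only mention of 2-hydroxyglutarate in the documents. No reason is given for choosing DNMT3A, and no measurement is planned for IDH-mutated patients as such.

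The same section summarises an earlier series of older AML patients given hypomethylating agents first line: "Among the 68 patients (median age 72 years; range, 60 - 83) with available data", 11 had an IDH1 or IDH2 mutation (16%), and "10 patients (15%) had DNMT3A mutations with 5 patients (7%) having both IDH and DNMT3A mutations".

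Section 7.4 orders the relevant genotyping before therapy: "Molecular studies in bone marrow specimens for FLT3-ITD, FLT3-TKD, NPM1, IDH1, IDH2, DNMT3A, TET2, EZH2, RAS, JAK2". IDH status should therefore be known at baseline.

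Section 1.3 lists the tertiary correlates as methylation, somatic mutations, micro-RNA and immune effector function. 2-hydroxyglutarate is not named there, and section 11.5 describes no analysis of it.

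**The concern.** The assay population is chosen by one gene, while the metabolite is the product of others. Mutant IDH1 or IDH2 produces 2-hydroxyglutarate; mutant DNMT3A does not. Two things follow if the sentence is carried out literally. IDH-mutated patients without a DNMT3A mutation are never assayed, although a raised level is expected in them. DNMT3A-mutated patients without an IDH mutation are assayed, although only background levels are expected. Variation in 2-hydroxyglutarate within the measured group would then largely show who also carries an IDH mutation, and an association with response would be read from only part of the relevant patients.

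Section 6.1 discusses IDH1/2 and DNMT3A side by side throughout, so a slip of gene name is the likeliest explanation. If DNMT3A was intended, the protocol needs to say why.

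**Working it through.** **Inputs.** From section 6.1: N = 68 patients, I = 11 IDH1/2-mutated, D = 10 DNMT3A-mutated, B = 5 with both. From section 11.1: a maximum of 100 patients. From Table 2: expected patients per arm.

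**Step 1: reproduce the stated percentages.** 11/68 = 16.2%, 10/68 = 14.7%, 5/68 = 7.4%. These match the stated 16%, 15% and 7%.

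**Step 2: cross-classify.** I read the 5 double mutants as included in both the 11 and the 10, which is the natural reading.

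| | DNMT3A mutated (assayed) | DNMT3A wild type (not assayed) | Total |
|---|---|---|---|
| IDH mutated | 5 | 6 | 11 |
| IDH wild type | 5 | 52 | 57 |
| Total | 10 | 58 | 68 |

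**Step 3: the two proportions.** Exact (Clopper-Pearson) 95% limits for x of n are the 0.025 quantile of Beta(x, n − x + 1) and the 0.975 quantile of Beta(x + 1, n − x).

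- IDH-mutated patients missed: (I − B)/I = 6/11 = 54.5%, CI 23% to 83%.
- Assayed patients without an IDH mutation: (D − B)/D = 5/10 = 50%, CI 19% to 81%.

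If the 5 double mutants were instead additional patients, the figures would be 11/16 = 69% and 10/15 = 67%, a larger mismatch.

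**Step 4: scale to this trial.** Expected count = trial total × count/68, assuming the earlier series' mutation frequencies carry over. Table 2 gives expected totals of 21.5 + 22.6 = 44.1 for response rates of 0.1 and 0.3, and 40.2 + 40.3 = 80.5 for 0.3 in both arms.

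| Trial total | IDH-mutated (×11/68) | DNMT3A-mutated, assayed (×10/68) | Both (×5/68) | IDH-mutated, missed (×6/68) |
|---|---|---|---|---|
| 44.1 | 7.1 | 6.5 | 3.2 | 3.9 |
| 80.5 | 13.0 | 11.8 | 5.9 | 7.1 |
| 100 | 16.2 | 14.7 | 7.4 | 8.8 |

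So about 4 to 9 of about 7 to 16 IDH-mutated patients would not be measured. The smallest Table 2 total, 20.1 + 20.1 = 40.2 for rates of 0.05 and 0.1, gives 6.5 IDH-mutated and 3.5 missed, which leaves the rounded range unchanged.

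**Step 5: size after the change.** Assaying all IDH-mutated patients plus the DNMT3A-only patients means I + (D − B) = 11 + 5 = 16 of 68. At 100 patients that is 16.2 + 7.4 = 23.5 (before rounding of the terms), against 14.7 now. The difference is the 8.8 IDH-mutated patients currently left out.

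**The case against.** The strongest objection is that the documents never say which mutation produces 2-hydroxyglutarate, so the plan does not contradict itself. That is correct, and the point depends on a premise from outside the documents. The premise is undisputed general biochemistry and not a result recalled from a particular study, so the point stands, but as a probable slip to be corrected or justified.

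The second objection is weight. This is one sentence on a metabolite outside the correlates named in section 1.3, with no analysis in section 11.5. The main question of section 6.1, how mutations relate to outcome, is untouched because IDH1 and IDH2 are to be tested anyway. This stands in full and sets the ceiling on importance.

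Third, several stronger readings are tempting and do not hold:

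- *Half of those measured are uninformative.* DNMT3A-mutated patients without an IDH mutation can serve as a background comparison. The plan describes no such comparison, but the samples would not be wasted.
- *The biomarker question could not be answered.* The association the sentence describes, within DNMT3A-mutated patients, can be computed. The corrected version would also be small: at the 30% response rate assumed in section 11.3, 16.2 IDH-mutated patients give 16.2 × 0.3 = about 5 responders. Either version is hypothesis-generating.
- *Most IDH-mutated patients would be absent.* The point estimate is 55%, but the interval of 23% to 83% does not establish a majority.
- *No sample is assigned, so the assay cannot be done.* Sections 7 and 8 name no aliquot for it. However, section 6.0 plans blood and marrow before, during and after treatment, and section 6.4 plans blood, marrow and plasma collection. An unnamed aliquot for one exploratory assay is missing detail.

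**Conclusion.** The point holds in limited form. As written, section 6.1 selects patients for 2-hydroxyglutarate by a gene that does not produce it, without a stated reason. By the protocol's own earlier counts, about half of the IDH-mutated patients would be left out and about half of those assayed would have no IDH mutation. Both fractions rest on only 10 or 11 patients, with intervals of roughly 20% to 80%, so they are expectations and not known figures for this trial.

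The conclusion assumes that mutant IDH1/IDH2 is the source of the metabolite, that the double mutants are counted within both mutation groups, and that mutation frequencies in this trial resemble the earlier series. That series was aged 60 to 83, whereas section 4.1 also admits younger patients. The projected counts further assume that every eligible patient yields a sample. Nothing in the primary or secondary endpoints, sample size, stopping rules or error rates is affected.

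**What to change.** Reword the sentence in section 6.1 so that 2-hydroxyglutarate is measured in patients with an IDH1 or IDH2 mutation, with DNMT3A-mutated, IDH-wild-type patients kept as a limited comparison group. If DNMT3A was deliberate, state the rationale instead.

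Take samples only at times already scheduled. An assay at every follow-up marrow should not be tied to the immune-function blood: marrows fall every 1 to 3 courses (8.3), but that blood is drawn at remission, relapse and about every 3 to 4 cycles (8.8), so the times would often not match.

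The cost is a wording change plus a few assays. IDH1/IDH2 status is already collected under 7.4. At 100 patients, about 16 IDH-mutated and about 7 DNMT3A-only patients would be assayed, against about 15 patients now. Repeat measurements would add to this in proportion. Using all IDH-wild-type patients as the comparison would be much larger (100 − 16.2 = about 84 patients) and is not needed.
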